4.5.2 Analysis

We will use interrupted time-series analyses (ITS) to investigate the impact of Respect implementation on key outcomes in the National Cardiac Arrest Audit, in particular, the proportion of resuscitation attempts that are terminated due to futility. The primary analysis will be a comparison of the group implementing the new ReSPECT form within three to nine months of the national implementation pre- and post-implementation. We anticipate that a period of between three and six months (depending on the speed at which the pilot/phase one is implemented) will need to be omitted from the data used for the interrupted time series analysis in order to ensure comparison of clean pre- and post- intervention periods. This analysis will compare predicted outcomes based on the model fitted to data from the pre-implementation period (i.e. we assume that the trend observed in the pre-implementation period is continued post implementation to estimate outcomes in the post- implementation time period, which is equivalent to assuming the new ReSPECT forms have no effect). As a secondary analysis we will examine actual (contemporaneous) outcomes in hospitals intending to keep using the old DNACPR forms.

197 hospitals contribute data to the NCAA programme in the UK and we will be able to obtain monthly data. By the time we come to perform the ITS analysis we will have at least 2 years (but possibly up to 5 years) of full NCAA data from the pre- implementation period and 1-2 years post-implementation. We will therefore have a minimum of 8 time points in each of the pre- and post- intervention time periods, as required for best performance of the ITS method.

The primary analysis will be performed using the ITSA command within Stata 13 with the Cumby-Huizinga test used to test for autocorrelation and determine the autocorrelation structure (identify the appropriate lag). The regression models will be calculated with Newey-West standard errors to deal with the autocorrelation and possible heteroscedasticity. Estimates of the model parameters (as appropriate) will be reported with associated 95% confidence intervals. Estimates of the trend in outcome during the post intervention period will also be reported with associated 95% confidence intervals. The results will also be presented graphically with observed and fitted data from the pre- and post-intervention periods plotted over time (quarterly) to illustrate the model fit and parameters estimated, with

appropriate counter factual information.

Sensitivity Analyses

We will explore the impact of choosing a longer or shorter implementation period to be omitted from the analysis. This will provide reassurance that the pre- and post-

implementation periods are correctly identified. We will also investigate whether outcomes within patient subgroups, defined by hospital type, age, reason for admission, are consistent

with our primary results.

Secondary analyses

The same (ITSA) approach will be used to investigate the impact of the intervention on vital

status at hospital discharge (% alive), proportion of resuscitation attempts that are terminated

due to presence of a DNACPR and proportion of cardiac arrests attended by the team that are shockable. The rate of in-hospital cardiac arrests attended by the resuscitation team per one

thousand admissions over time will also be plotted over time to illustrate changes in slope and

trend. Data on patient status at team arrival (dead – resuscitation stopped, resuscitation

ongoing, ROSC achieved before team arrival, deteriorating (not yet arrested)), Cerebral

Performance Category at discharge (Alive-1, Alive-2, Alive-3, Alive-4), the rate of in-hospital

cardiac arrests and variance in the proportion of resuscitation attempts that are terminated

due to futility over time will also be presented using appropriate descriptive methods.

The annual survey will be analysed descriptively and information about type of system used

(e.g. DNACPR, other ECTP system or ReSPECT) and date when ReSPECT was implemented will

be linked to the NCAA data to facilitate the ITS analysis using comparison groups described

above.

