4.3 Data Collection for WP2

NCAA collects data on hospital characteristics and individual patient demographic, resuscitation process and outcome variables for patients who sustain an in-hospital cardiac arrest and receive resuscitation by the hospital resuscitation team (or equivalent). Standardised case identification methods, data definitions, online and manual data validation ensures consistent, high quality data are collected. The NCAA Steering Committee has approved this study and for us to access the data. A sample of data will be transferred to allow the development and testing of statistical code before the final data transfer of the complete anonymised NCAA data set.

Our national audit (2014) indicates that approximately 80% of Acute NHS Trusts use the national DNACPR form (or a modified version) for making resuscitation decisions with the remainder using a system similar to the planned ReSPECT process. Although the new ReSPECT form and supporting documentation will be made available nationally in 2017, the time taken to incorporate into local Trust policies is likely to be variable. To establish baseline systems and time of change to ReSPECT we will contact the NCAA contact at each participating hospital at the start of the study and annually thereafter. The initial survey will establish (i) what system is currently in use at that Trust and how long it been in use (ii) when training for ReSPECT started (iii) when ReSPECT were first implemented (iv) when the entire organisation had adopted the ReSPECT form (v) proportion of patients who have a ReSPECT decision. Freedom of Information request will be made to each hospital, to gain as near complete information as possible in the final year of the study, since the initial survey did not yield a sufficient response rate to enable accurate analysis of the NCAA audit data.

Centres which switch from using a system of DNACPR decisions to ReSPECT between three and nine months of the launch of the national form will form the focus for the interrupted time series analysis. It is possible that some Acute NHS Hospital Trusts will not adopt the ReSPECT form or adoption may be very delayed. In this event such sites will be reported separately as observed counterfactual information.

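### WP2: agreement between different omitted-window lengths cannot by itself reassure that the before and after periods are placed correctly

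*Protocol*

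**What the plan says.** Section 4.5.2 leaves the roll-out phase out of the series: "We anticipate that a period of between three and six months" is to be omitted so that the before and after periods are clean. Under Sensitivity Analyses it adds: "We will explore the impact of choosing a longer or shorter implementation period to be omitted from the analysis". The next sentence gives the purpose. It begins "This will provide reassurance that the pre- and post" and ends "implementation periods are correctly identified". It does not depend on what the analysis shows.

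The dates come from section 4.3. A survey asks each hospital for training start, first implementation, whole-organisation adoption and the proportion of patients with a ReSPECT decision. Freedom of Information requests are added in the final year, "since the initial survey did not yield a sufficient response rate to enable accurate analysis of the NCAA audit data". The same dates decide who is analysed: "Centres which switch from using a system of DNACPR decisions to ReSPECT between three and nine months of the launch of the national form" are the focus of the analysis.

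**The concern.** A window-length analysis changes how many months are dropped around a recorded date. It does not change the recorded date, and it does not change which hospitals are in the analysed group. Stable results therefore show that the estimate is not sensitive to the cut. They do not show that the cut is in the right place.

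This matters because the protocol itself says that its first source of dates was inadequate. If misdating diluted the effect, the windows could agree on a result near zero. The protocol's sentence would then support reading that as good evidence that ReSPECT did not change the proportion of attempts stopped for futility.

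**Working it through.** The protocol gives no agreement rate, effect size or volume for this check, so there is no stated figure to reproduce.

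**Inputs from the protocol**
- Baseline proportion 6.5% (section 4.1.2).
- Monthly data, segmented linear model, Newey-West standard errors (section 4.5.2).
- Series length: "at least 2 years (but possibly up to 5 years) of full NCAA data from the pre- implementation period and 1-2 years post-implementation". I use 24 months before and 24 after, then 12 after.

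**Assumptions (not in the protocol)**
- A true fall of 2 points, to 4.5%.
- 120 or 400 attempts per month in the pooled group.
- Windows of 3, 6 and 9 months running forward from the recorded date.

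**Step 1: no effect.** The expected series is one straight line, so the expected level change is 0 for every window and every set of true dates. Agreement carries no information about dates.

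**Step 2: real effect, expected values.** Number the months 0 to 47, with the recorded date at 24. Omit w months. The level change is taken at the first retained month, r = 24 + w, against the projected pre-trend. The expected series is 6.5 - 2f(t), where f(t) is the share of hospitals that have adopted.

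Hand check for adoption 6 months before the recorded date:
- Pre-period mean = 6.5 - 2 × 6/24 = 6.0.
- Pre-period slope = -2 × 54/1150 = -0.0939 per month. Here 54 is the sum of the deviations of months 18 to 23 from the mean month 11.5, and 1150 is the sum of squares of the 24 months.
- Projection at month 30 = 6.0 - 0.0939 × 18.5 = 4.26.
- Level change = 4.5 - 4.26 = +0.24.

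Least squares on the noise-free series gives these level changes in points:

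| True adoption | w = 3 | w = 6 | w = 9 |
|---|---|---|---|
| As recorded | -2.00 | -2.00 | -2.00 |
| 6 months earlier | -0.04 | +0.24 | +0.52 |
| 12 months later | +0.26 | -0.07 | -0.70 |
| Scattered, SD 9 months | -0.54 | -0.60 | -0.61 |
| 6 months later, all hospitals | -1.01 | -2.00 | -2.00 |

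**Step 3: compare with sampling error.** For w = 6, the variance factor of the level change is 1/24 + 18.5²/1150 + 1/18 + 8.5²/484.5 = 0.0417 + 0.2976 + 0.0556 + 0.1491 = 0.544, with square root 0.738.
- At 400 attempts: monthly SD = √(0.065 × 0.935/400) = 1.23 points, so the 95% half-width is about 1.96 × 0.738 × 1.23 = 1.78 points.
- At 120 attempts: monthly SD is 2.25 points, so the half-width is about 3.25 points.

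These use the baseline rate throughout and no autocorrelation. In the first four rows the largest expected move away from the 6-month estimate is 0.63 points (from -0.07 to -0.70), well inside either half-width.

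**Step 4: simulation, 24 months after.**
- Counting agreement as all windows lying inside the 6-month window's 95% CI, the rate was about 98 to 100% with correct dates and in the three misdated rows (6 months early, 12 months late, scattered).
- With 40 hospitals, 7 arrests per hospital-month and a 20% relative reduction, the significance verdict on the level change agreed in 79% of runs with correct dates. It agreed in 81 to 85% with one third of hospitals misdated, all misdated by up to 12 months either way, all 12 months late, or half never adopting.
- When wrong dates hid the effect in that example, the other windows missed it too in 89 to 91% of runs.
- With one third of hospitals misdated, the shift between windows separated wrong from correct dates with an area under the curve of 0.49 to 0.53, where 0.5 is no information.

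**Step 5: where the check reacts.**
- A shared 6-month delay moves the 3-month window to -1.01 while the others stay at -2.00. CI agreement then ran from 40% to 97% across the settings tried.
- With a 40% reduction, 12 arrests per hospital-month and all dates 6 months late, the level-change verdict agreed in only 20 to 28% of runs.
- With 12 months after, agreement is lower in general. In one setting (40 hospitals, 12 arrests, 20% reduction, windows of 6 and 3 months) the verdict agreed in 73% with correct dates and 74 to 80% with wrong dates.

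**The case against.** A reader might infer that the windows agree almost always, so that the check is empty. The calculations do not support that. The 98 to 100% figures rest on a CI-overlap criterion that the protocol does not state, on windows that share most of their data, and on 24 months after, whereas the protocol allows 12. A shared delay is often picked up.

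A reader might also infer that the protocol treats this analysis as proof, or as its source of dates. It does neither. It speaks of exploring and of reassurance, collects dates directly in section 4.3, and uses Freedom of Information requests to repair the poor survey response. Section 4.5.2 also plots observed against fitted values and looks at hospitals keeping the old forms. Nothing says that a null result would be published with a claim that the dates were verified.

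Some misdating scenarios are strained. The analysed group switches 3 to 9 months after launch, so adoption 6 months before a recorded date under 6 months would precede launch, apart from the 2016 pilot. With SD 9 months around a date 6 months after launch, about 25% of hospitals would do so. The protocol does not say that the window grows only forward.

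Finally, window lengths and agreement criteria belong in the SAP, which section 4.5.1 promises. Their absence is not the point.

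All of this stands, and it limits the size of the point. It does not repair the sentence: what the protocol says window length can reassure about is wrong whatever detail a SAP adds. The no-effect argument in Step 1 needs no scenario at all.

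**Conclusion.** The point holds in a limited form. Agreement across window lengths cannot by itself support the statement that the periods are correctly placed. With no effect it says nothing about dates. With a real 2-point fall, 24 months after and the volumes assumed, scattered dates shrink the 6-month estimate to about -0.6 and a 12-month delay takes it to about -0.1, and the windows agree about as often as with correct dates.

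These sizes depend on the number of early adopters, attempts per month, effect size and pattern of date error, none of which the protocol gives. No single agreement rate should be quoted. The statement should be changed because the weak survey response makes misdating a live risk and the correction is cheap. It is not evidence that the primary analysis is invalid.

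**What to change.** 1. In section 4.5.2, replace the sentence on reassurance with: *This tests robustness of the estimate to the length of the omitted window.*
2. Add sensitivity runs that move each hospital's interruption between the dates requested in section 4.3: training start, first implementation and whole-organisation adoption.
3. Add one run that excludes hospitals whose dates are missing or conflict between the survey and the Freedom of Information reply.

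The cost is a wording change and a few extra runs on data already requested. The run in item 3 may have fewer hospitals and wider intervals. The report gives up any suggestion that the outcome data confirmed the periods.

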A training / implementation package is being developed for simultaneous launch by the national working group. It is envisaged that changes in a patients' circumstances (e.g. acute admission to hospital, the presence of a new, life limiting diagnosis, acute deterioration overall decline in functional status) will prompt consideration of emergency care treatment plan choices. Experience with the UFTO system indicates that around 70% of in-patients will have a ReSPECT process completed at the time of hospital admission of which approximately 20% will also have a DNACPR decision.

In this research we recognise that the intervention being evaluated may be under specified and that a form cannot achieve change by itself – human agency is involved. The form could be seen as analogous with the checklist in the Michigan sepsis study which resulted in a large and sustained reduction (up to 66%) in rates of catheter related bloodstream infection. [34]

However the Michigan study was subsequently shown to be a compound intervention involving not just the form but a cultural change intervention. [35] Introducing the ReSPECT is also likely to be associated with other actions. Part of our plan is therefore to capture how the ReSPECT was implemented in the sample sites in field notes (WP1) and through summary data collected at regular meetings between site representatives, researchers and members of the ReSPECT National Working Group (WP4).

Figure 1 ReSPECT Evaluation flow diagram

Aims and Objectives

- Describe the clinician decision making processes (WP1a & WP1b)
- Quantify the effect of ReSPECT on the frequency of and outcomes from in-hospital resuscitation attempts (WP2)
- Determine the influence of ReSPECT decisions on quality measures (NHS safety thermometer) (WP3)
- Synthesise key findings and effectively disseminate, ensuring that key messages are integrated into future development work of ECTPs (WP4)

WP1a & WP1b- Evaluation of ReSPECT clinical decision-making at 6 NHS acute hospitals

WP1a

- Observation of clinician decision-making and interviews
- Interviews with patients/relatives *WP1b*
- Ethical basis and the experience of patients/relatives in the decision-making process

WP 2 - Effect of ReSPECT on frequency of and outcomes from in-hospital resuscitation (National audit)

Recruitment of 6 sites, ethics, governance and set up processes

- Rate of in-hospital arrests attended by the resuscitation team per 1000 admission
- Patients status at team arrival

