4.1 Study Design

4.1.1 Objective

To quantify the effect of the introduction of ReSPECT on frequency of and outcomes from, inhospital resuscitation attempts.

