4.1.2 Rationale

A key concern of patients and relatives who contacted an end-of-life support line during our scoping review was that they would be subjected to resuscitation when it had little to no chance of success. [9] The National Confidential Enquiry into Patient Outcomes and Death (NCEPOD) report identified that resuscitation decisions were often not considered in patients admitted to hospital. [6] A key reason for this was their binary nature (for resuscitation or DNACPR) which does not allow decisions to be contextualised with other treatments. This meant that a large proportion of resuscitation attempts were undertaken in those where the NCEPOD reviewers considered a DNACPR decision should have been made prior to the cardiac arrest. These findings are consistent with data from National Cardiac Arrest Audit (NCAA) (2015-16) indicates that 6.5% of resuscitation attempts were terminated after arrival of the resuscitation team as they considered it was futile to continue.

We hypothesise that if the ReSPECT process is successful in allowing resuscitation decisions to be contextualised to overall treatment plans, the proportion of resuscitation attempts terminated by the resuscitation team as they consider resuscitation as futile will decline, the total number of resuscitation attempts will reduce and the proportion of patients, on whom CPR is attempted, surviving to go home from hospital (and their functional status) will improve.

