4.3.1 Outcome measures

Primary: Proportion of resuscitation attempts that are terminated due to futility

Secondary:

- (i) Number of in-hospital cardiac arrests attended by the resuscitation team per one thousand admissions
- (ii) Patient status at team arrival (dead resuscitation stopped; resuscitation ongoing; ROSC achieved before team arrival; deteriorating (not yet arrested))
- (iii) Proportion of resuscitation attempts that are terminated due to presence of a DNACPR (this represents a failure of implementation)
- (iv) Vital status at hospital discharge (alive or dead)
- (v) Proportion of shockable arrhythmic cardiac arrests
- (vi) Cerebral Performance Category at discharge
- (vii) Proportion of cardiac arrests to total number of hospital deaths

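### WP2 sets out to quantify the effect of ReSPECT on how often resuscitation is attempted, but the plan only plots and describes that rate and specifies no estimate or interval for it

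*Protocol*

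**What the plan says.** Protocol section 4.1.1 gives WP2 one objective: "To quantify the effect of the introduction of ReSPECT on frequency of and outcomes from, inhospital resuscitation attempts". The aims listed with Figure 1 in section 2.1 repeat it. Section 4.1.2 hypothesises, among other things, that "the total number of resuscitation attempts will reduce".

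Section 4.3.1 lists the outcomes. The primary is given as "Primary: Proportion of resuscitation attempts that are terminated due to futility". Secondary outcome (i) is the frequency measure: "Number of in-hospital cardiac arrests attended by the resuscitation team per one thousand admissions".

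Section 4.5.2 assigns the analyses:

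- The primary proportion gets the ITSA regression with Newey-West standard errors, and model parameters are reported with 95% confidence intervals.
- Under the secondary analyses, one sentence opens "The same (ITSA) approach will be used to investigate the impact of the intervention on vital" and goes on to name vital status at discharge (as percent alive), the proportion of attempts stopped because a DNACPR was present, and the proportion of attended arrests that are shockable.
- The attended-arrest rate comes in the next sentence, per one "thousand admissions over time will also be plotted over time to illustrate changes in slope and" trend.
- The sentence after that places the rate of in-hospital cardiac arrests among items to be presented by descriptive methods.

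**The concern.** The objective promises a quantified effect on frequency, and the rationale states a direction for it. The analysis section gives that outcome no fitted model, effect estimate or interval. Section 4.5.1 argues for interrupted time series because the method allows for trends already present before implementation. A plot without a model does not do that. If the attended-arrest rate was already moving, a reader of the plot could not separate that drift from a change at implementation, or judge how uncertain the change is.

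The modelled outcomes do not fill the gap. Section 4.3 says the audit holds only patients who arrest and are resuscitated by the team. All four modelled outcomes are therefore proportions within a group whose size ReSPECT is expected to reduce. What is at stake is whether WP2 can answer the frequency part of its objective, and whether movements in the proportions can be interpreted without it.

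**Working it through.** WP2 gives no sample size, power or effect size, so there is no figure of the plan's own to reproduce. The check sets the text side by side and then does simple denominator arithmetic.

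**Text.**

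| Outcome | Denominator | Analysis in 4.5.2 |
|---|---|---|
| Stopped for futility (primary) | attempts | ITSA, 95% CI |
| Alive at discharge | attended arrests | ITSA |
| Stopped because of a DNACPR | attempts | ITSA |
| Shockable rhythm | attended arrests | ITSA |
| Attended arrests per 1000 admissions, outcome (i) | admissions | plot |

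The only outcome in this table that measures frequency is the only one without a model.

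**Inputs for the arithmetic.** The baseline futility proportion is 6.5% (section 4.1.2, audit data for 2015-16), which is 65 per 1000 pre-period attempts. The sizes of the falls below are assumptions, because the documents give none.

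**Formula.** Let a share f of futile attempts and a share g of the other 935 attempts be avoided. The primary proportion becomes 65(1−f) / [65(1−f) + 935(1−g)].

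| f | g | Attempts left | Primary | Fall in attempts |
|---|---|---|---|---|
| 20% | 20% | 52 + 748 = 800 | 52/800 = 6.50% | 20% |
| 30% | 20% | 45.5 + 748 = 793.5 | 45.5/793.5 = 5.73% | 20.7% |
| 10% | 20% | 58.5 + 748 = 806.5 | 58.5/806.5 = 7.25% | 19.4% |
| 25% | 0 | 983.75 | 48.75/983.75 = 4.96% | 1.6% |
| 50% | 0 | 967.5 | 32.5/967.5 = 3.36% | 3.2% |
| 75% | 0 | 951.25 | 16.25/951.25 = 1.71% | 4.9% |

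Falls in attempts of about 20% go with a primary that is unchanged, lower or higher. Large drops in the primary go with falls in attempts of under 5%. The proportion does not determine the frequency effect.

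**Break-even.** If R attempts are avoided and a share s of them would have been stopped for futility, the primary becomes (65 − Rs)/(1000 − R). This is below 6.5% exactly when s exceeds 6.5%.

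**Survival.** Take 17% at baseline. This comes from the single-hospital internal evaluation in section 1 and is used only as an illustration. Avoiding 20% of the 830 non-survivor attempts gives 170/(170 + 664) = 170/834 = 20.4%, with the same 170 survivors. Percent survival also needs the rate beside it.

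**The case against.** The best case for the text as it stands has four parts.

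1. Section 4.5.2 applies interrupted time series to key outcomes in general. The sentence on the rate follows directly after the ITSA list and speaks of slope and trend, which are the terms of a segmented model. The later descriptive item does not say that it is the same rate. This leaves some ambiguity. But the ITSA list is explicit and omits the rate, and the verb used is to plot, so the natural reading is that no model is intended. A later SAP could add one, but the protocol has already assigned a descriptive analysis here.

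2. Frequency is not ignored. It is a named secondary outcome shown over time, so it would be too much to say that half the objective goes unanswered. What is missing is the trend-adjusted estimate and its interval.

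3. A reader might infer that the primary and survival outcomes are invalid because ReSPECT shrinks their denominator. The protocol does not support that. Section 4.1.2 states both hypotheses conditionally on an attempt, and better selection of who receives CPR is the proposed mechanism. A rise in percent survival without extra survivors is compatible with what it predicts.

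4. The flat and rising cases require other attempts to be avoided at least as strongly as futile ones. The break-even share of 6.5% is a low bar for a process aimed at futile attempts, and when only those are avoided the primary falls as intended. This stands. The scenarios show that the proportion cannot replace the rate, not that the primary is likely to mislead.

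**Conclusion.** The mismatch holds. The protocol sets out to quantify an effect on frequency and predicts its direction, then assigns the frequency outcome a plot and descriptive presentation, with no level or slope change and no 95% confidence interval. The modelled proportions cannot supply the missing result: an even 20% fall in attempts would leave the primary at 6.5%.

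This should be corrected, but it is not a fatal flaw. The primary outcome and its analysis are unaffected, and frequency would still be reported over time. The conclusion about the text rests on reading the ITSA list in 4.5.2 as complete. The arithmetic rests on the protocol's 6.5%, on assumed falls in attempts, and, for survival, on a single-hospital 17%. The documents give no baseline attended-arrest rate or variance, so the precision of a modelled rate cannot be calculated.

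**What to change.** In section 4.5.2, add secondary outcome (i) to the outcomes analysed with the same ITSA model, and state that its level and slope changes will be reported with 95% confidence intervals. Add a sentence saying that the primary proportion and percent survival will be interpreted beside that result. Make clear whether the rate of in-hospital cardiac arrests in the descriptive list is the same quantity. Leave the primary outcome as it is.

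Futility terminations and survivors to discharge, each per 1000 admissions, could be added as supportive series. They are optional: section 4.3.1 does not list them, and they correct no contradiction.

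The cost is a change of wording and one more secondary model. The admissions denominator is already needed for outcome (i). Section 4.5.1 requires an approved SAP before the time series analysis, so the change can be made then.
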